6.1 Screened Analysis Set

The screened Analysis Set consists of all subjects who provide written informed consent.

6.2 Randomized Analysis Set

The Randomized Analysis Set is comprised of all subjects in the Screened Analysis Set who were randomized. Any subject who provides written informed consent and is assigned a treatment randomization number will be considered to have been randomized. This Analysis Set will be used to describe the disposition of study participants enrolled in the study.

6.3 Intent-to-Treat Analysis Set

The ITT Analysis Set is comprised of all subjects in the Randomized Analysis Set with the exception of subjects enrolled at site(s) excluded from analysis due to potential study misconduct. The ITT Analysis Set will utilize the treatment to which the subject was randomized regardless of the treatment actually received. This Analysis Set will be used to describe the study population and in the analyses of efficacy endpoints.

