**10.2.2 Intent-to-Treat Analysis Set**

The Intent-to-treat (ITT) Analysis Set comprises all subjects in the Screened Analysis Set who were randomized. The ITT Analysis Set will be analyzed using the treatment to which the subject was randomized, regardless of the treatment actually received.

Any subject who receives a treatment randomization number will be considered to have been randomized.

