#### **10.2.4 Safety Analysis Set**

The Safety Analysis Set comprises all subjects in the ITT Analysis Set who receive any amount of the investigational product, and will be based on the actual treatment received. The safety set will be the primary analysis population for safety data.

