4.6.2 Interim Sample Size Re-estimation

MACE rates will be monitored by CSLB and the Executive Committee, using blinded data, to reach a decision on the final sample size prior to completion of the enrollment phase. The observed blinded event rate will be based on a 90-day Kaplan-Meier estimate using a time-to-event approach with appropriate censoring to account for unobserved data. If the observed blinded event rate is higher than expected, then fewer subjects than 17,400 may be enrolled, with a minimum of approximately 15,000 subjects, corresponding to a placebo 90-day event rate of 7.4%. Conversely, if the observed, blinded event rate is less than expected, more subjects may be enrolled, but the increase would be capped at approximately 20,600 subjects, corresponding to a placebo 90-day event rate of 5.4%. The decision regarding sample size adjustment will be made when approximately 75% of subjects have been enrolled or approximately 75% of events have been accrued, whichever occurs first, with communication to sites occurring approximately 3 months prior to close of enrollment. The actual number of subjects to be enrolled, within the pre-specified range (15000 to 20600), will be determined by the Executive Committee and sponsor and chosen to provide a total of approximately 1004 events for the primary outcome. A subgroup analysis will be performed at the time of

final reporting to assess the consistency of primary MACE results for cohorts enrolled before and after the site communication on sample size re-estimation.

The table below illustrates the sample size associated with hypothetical placebo 90-day event rates assuming a 20% risk reduction attributable to CSL112. Since the sample size re-estimation will be performed using blinded data, the observed event rate will be compared to the pooled event rate shown in Table 4-3 below.

Table 4-3 Event Rate for Re-estimating Sample Size

Event Rate (%)			Sample Size
Placebo	CSL112	Pooled	
7.40	5.92	6.66	15,000
6.40	5.12	5.76	17,400
5.40	4.32	4.86	20,600

5 Changes in the Conduct of Protocol Planned Analyses

Not applicable

6 Study Analysis Sets

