6.4 Modified Intent-to-Treat Analysis Set

The modified Intent-to-treat (mITT) Analysis Set is comprised of all subjects in the ITT Analysis Set who receive any amount of investigational product. The mITT Analysis Set will be analyzed using the treatment to which the subject was randomized, regardless of the treatment actually received.

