6.5 Safety Analysis Set

The Safety Analysis Set is comprised of all subjects in the ITT Analysis Set who receive any amount of the investigational product, and will be analyzed based on the actual treatment received. The safety Analysis Set will be the primary population for summarizing and reporting safety data.

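### The SAP lets whole sites be removed from the set it still calls ITT, and from mITT and Safety with it; no planned efficacy or safety analysis covers all randomized or all dosed subjects, and SAP Section 5 reports no change

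*SAP*

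**What the plan says.** **Protocol (Amendment 1).** Section 10.2.2: "The Intent-to-treat (ITT) Analysis Set comprises all subjects in the Screened Analysis Set who were randomized". It adds: "Any subject who receives a treatment randomization number will be considered to have been randomized". There is no exclusion by site. Section 10.2.4 builds safety on that full set: "The Safety Analysis Set comprises all subjects in the ITT Analysis Set who receive any amount of the investigational product". Section 10.3.2 makes ITT the primary efficacy population.

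**SAP (version 4.0).** Section 3 says the SAP is based on protocol Amendment 1. Section 6.2 defines a Randomized Analysis Set of all randomized subjects and assigns it to disposition. Section 6.3 defines ITT as that set "with the exception of subjects enrolled at site(s) excluded from analysis due to potential study misconduct", and states: "This Analysis Set will be used to describe the study population and in the analyses of efficacy endpoints". The other two sets follow from it. Section 6.4: "The modified Intent-to-treat (mITT) Analysis Set is comprised of all subjects in the ITT Analysis Set who receive any amount of investigational product". Section 6.5: "The Safety Analysis Set is comprised of all subjects in the ITT Analysis Set who receive any amount of the investigational product". Section 11 bases all safety analyses on the Safety set.

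Section 5, headed "Changes in the Conduct of Protocol Planned Analyses", reads 'Not applicable'. The version history (Section 1, version 3.0, item 1) does record that a Randomized set was added because ITT may exclude sites.

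**The concern.** Both documents run the confirmatory test on a set called ITT, but the two definitions agree only if no site is excluded. A reader of the protocol would expect the primary hazard ratio to compare everyone randomized. Under the SAP it may not, and no planned result would show whether the exclusion changed the answer.

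The safety consequence is more direct. Doubt about a site's data can justify showing results without that site. It does not remove the fact that its subjects received infusions. Because Safety is drawn from the reduced ITT, the adverse events, serious adverse events, events of special interest and exposure of those subjects would be missing from every planned safety summary. The protocol's own Safety set would have included them.

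The trigger is also loosely worded. Misconduct need only be potential, and the SAP gives no criterion and names no one who decides.

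**Working it through.** **1. The sets side by side**

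| Set | Protocol | SAP |
|---|---|---|
| All randomized | Is the ITT set (10.2.2) | Randomized set, used for disposition (6.2, 9) |
| ITT | All randomized | Randomized minus subjects at excluded sites (6.3) |
| mITT | Dosed subjects in all-randomized ITT (10.2.3) | Dosed subjects in reduced ITT (6.4) |
| Safety | Dosed subjects in all-randomized ITT (10.2.4) | Dosed subjects in reduced ITT (6.5) |

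The wording of mITT and Safety is almost the same in both documents. Only the parent set differs, and that is enough to remove the excluded sites from all three.

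**2. Does any planned analysis recover the all-randomized comparison?** SAP Section 10.1.1 plans a tipping-point analysis, a reduced model, an unadjusted model, an mITT analysis and a per-protocol estimand. Section 7.1 adds a COVID-19 estimand. None is specified in the Randomized set. The primary estimand in Section 10.1 addresses non-initiation, missed doses and discontinuation, but not removed sites. In Section 11 no table is specified for dosed subjects outside the Safety set.

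**3. Size: effect on power.** The documents do not say how many subjects, if any, are affected, so a range has to be assumed.

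Inputs, from SAP Sections 4.5 and 4.6.1.1 and Table 4-3: hazard ratio 0.80, 1004 events, 17,400 subjects, 90-day rates of 6.4% and 5.12%, futility looks at 30% and 50%, an efficacy look at 70% with one-sided P < 0.000083, and final one-sided P < 0.024999.

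The plan's own figures first:
- Expected events: 17,400 × (0.064 + 0.0512)/2 = 1002, against 1004 stated.
- Simulated power, with the futility rule applied: 91.9%, as stated.
- Simulated cumulative futility: 0.040 at hazard ratio 0.8 and 0.735 at 1.0. Null rejection: 0.022. All three agree with SAP Table 4-2.

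Then the same simulation with an assumed fraction f of subjects and events removed, so that events = 1004 × (1 − f):

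| Assumed f | Subjects removed | Events left | Power at HR 0.80 |
|---|---|---|---|
| 1% | 174 | 994 | 91.7% |
| 2% | 348 | 984 | 91.6% |
| 5% | 870 | 954 | 91.0% |
| 10% | 1740 | 904 | 89.9% |

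**4. What one site contributes.** Protocol Section 3.1 plans about 1000 sites. An average site therefore holds 17,400/1000 ≈ 17 subjects and 1004/1000 ≈ 1 primary event. The documents give no individual site sizes, and a high-enrolling site would hold more.

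**The case against.** The strongest defence has four parts.

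*The exclusion is conditional.* This stands. The version history says sites may be excluded. If none is, the SAP and protocol sets have the same members and nothing is lost.

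*It is done blind.* This largely stands. SAP Section 3 places decisions on the final analysis before database lock, and Section 4.4 places formal unblinding after lock. Assignment is central, without regard to site. Removing a whole site without knowledge of treatment does not select by arm. What is missing is narrower: a criterion for potential misconduct and a named decision-maker.

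*It is disclosed.* This stands in part. The change is logged, subjects in each analysis set are counted, and those excluded are listed (SAP Section 9.1). Neither step supplies an efficacy or safety result, and neither corrects Section 5. Safety oversight during the trial is unaffected, because serious adverse event reporting and data monitoring committee review do not depend on the analysis set. The gap is in the planned final safety tables.

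*Excluding unreliable data from the primary analysis is defensible.* This also stands as a choice, provided the all-randomized result is shown beside it.

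A reader might infer that a few excluded events could manufacture significance. Take a hypothetical result near the boundary: 471 CSL112 and 533 placebo events, with z = ln(533/471)/√(1/471 + 1/533) = 1.955 (one-sided P 0.025). Removing a net 5 CSL112 events gives z = 2.12 (P 0.017). Removing a net 5 placebo events gives z = 1.80 (P 0.036). The shift can go either way, and near the boundary a few events decide any trial. If excluded events split about 1:1, the standard deviation of the net imbalance is the square root of their number. A net 5 is then one standard deviation only after about 25 events, or about 25 average sites. This shows fragility, not bias or type I error inflation.

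**Conclusion.** The point holds as a mismatch between the documents and a gap in the planned outputs. The SAP's primary population can differ from the protocol's. If it does, no planned efficacy analysis uses all randomized subjects, and dosed subjects at excluded sites are absent from every planned safety table, contrary to protocol Section 10.2.4. Section 5 is wrong to report no change.

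The documents do not support a claim that sites were in fact dropped, that the exclusion favours CSL112, or that the change was concealed. Power is not the issue: the loss is about 1 percentage point at an assumed 5% exclusion and about 2 points at 10%, on the assumption that subjects and events are lost in the same proportion and the hazard ratio is unchanged.

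**What to change.** 1. In SAP Section 10.1.1, pre-specify the primary Cox model in the Randomized Analysis Set as a mandatory sensitivity analysis if any site is excluded.
2. In SAP Section 6.5, define Safety as all dosed subjects in the Randomized set, analysed by treatment received. Present the site-excluded version as supportive.
3. In SAP Section 5, report that the primary population differs from protocol Section 10.2.2. Preferably give the site-excluded set a name other than ITT.

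A sentence in Section 6.3 stating the exclusion criterion, who decides, and that the decision is made blind to treatment would close the remaining gap in wording.

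The cost is SAP text now. If a site is excluded, it is also one extra model run and a second set of safety tables. If none is excluded, no further work is needed. Planned events, sample size and power do not change.

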6.4 Modified Intent-to-Treat Analysis Set

The modified Intent-to-treat (mITT) Analysis Set is comprised of all subjects in the ITT Analysis Set who receive any amount of investigational product. The mITT Analysis Set will be analyzed using the treatment to which the subject was randomized, regardless of the treatment actually received.

6.5 Safety Analysis Set

The Safety Analysis Set is comprised of all subjects in the ITT Analysis Set who receive any amount of the investigational product, and will be analyzed based on the actual treatment received. The safety Analysis Set will be the primary population for summarizing and reporting safety data.

6.6 PK Analysis Set

The PK Analysis Set will comprise all subjects in the safety Analysis Set who consent to participate in the PK sub-study and have one or more post baseline measurable (>0) plasma concentration of apoA-I or PC. For analyses and displays based on the PK population, subjects will be classified according to treatment received regardless of the treatment group to which they were randomized.

6.7 PD Analysis Set

The PD Analysis Set will comprise all subjects in the Safety Analysis Set who consent to participate in the PD sub-study and have one or more post-baseline measurable (>0) concentration for cholesterol efflux parameters. Subjects will be classified according to treatment received regardless of the treatment group to which they were randomized.

7 General Considerations

Analysis datasets will be created according to Clinical Data Interchange Standards Consortium, and data will be displayed according to reporting standards defined in this SAP and output (tables, listings, and figures) formats.

SAS version 9.3 or higher will be used to perform all data analyses and to generate tables, figures, and listings.

Continuous variables will be summarized in terms of the number of observations (n), mean, standard deviation (SD), median, Q1 (25th percentile), Q3 (75th percentile), minimum and maximum. Other descriptive statistics (eg, geometric mean, coefficient of variation) may be reported when appropriate.

Categorical variables will be summarized using frequency counts and percentages. Analyses that use other descriptive statistics will be identified with the analysis in the applicable SAP section.

Summary statistics of central tendency will be reported to one more decimal place than the collected data. Summary statistics of variability will be reported to one more decimal place than the commensurate measure of central tendency. For example, the mean and median for age will be reported to one decimal place because it is collected in full years. The standard deviation of age will then be reported to 2 decimal places. Descriptive percentages will be displayed to one decimal place. Displays of proportions will include 3 decimal places.

Durations (in days) for adverse events will be displayed to the nearest integer.

Formatting for dates and times will be:

Dates only – ddmmmyyyy

Times only – hh:mm

Dates and times – ddmmmyyyy hh:mm

In general, for by-visit summaries, data recorded will be presented by nominal visit.

Unscheduled assessments will not be included in by-visit summaries but will contribute to determination of Last Observed Value or End of Study Value. Unscheduled assessments will be included in data listings as well as the determination of best and worst case values.

All listings will be presented by treatment group and will include subject number.

Assessment windows will not be defined for the purpose of classifying measurements obtained outside scheduled assessment times.

Deviations from the analyses in this SAP will be identified in the clinical study report.

7.1 COVID-19 Impact

During the course of this study, the global COVID-19 pandemic occurred, impacting the study in a variety of ways. This section describes how the impact of COVID-19 will be reported.

Subject Disposition: Study Treatment Discontinuation or Study Discontinuation

If IP or study discontinuation is due to “subject decision”, “withdrawal by subject”, “physician decision”, or “other” reason, then additional free text to indicate the relationship to COVID-19 will be captured on the IP disposition and study conclusion eCRF forms. The associated free text entry will include character string(s) related to “COVID-19” to allow identification of subjects discontinuing due to the pandemic.

If the reason for IP/study discontinuation is a non-fatal AE or death or an endpoint event that was negatively adjudicated, then the identifier of the specific AE resulting in discontinuation will be captured. Discontinuations due to COVID-19 will then be identified based on whether the corresponding preferred term is included in the COVID-19 standard MedDRA query (SMQ) narrow.

Cases of study treatment discontinuation or study discontinuation due to COVID-19 will be included in the summary of subject disposition.

Demographic and Baseline Characteristics

Demographic and baseline characteristics will be summarized by COVID-19 period, ie before and after pandemic onset. This will allow an assessment of whether subject characteristics changed after pandemic onset. For purposes of these summaries, COVID-19 pandemic onset will be considered to be 11 March 2020 which corresponds to the pandemic declaration date by the World Health Organization (WHO).

Subjects with enrollment date on or after the pandemic onset will be flagged in the listings of demographic and baseline characteristics.

Adverse Events

Adverse events associated with COVID-19, which can include a clinically significant laboratory finding like a positive test result for COVID-19, will be reported by investigators

following requirements outlined in the protocol. COVID-19 associated adverse events will be identified via MedDRA coding based on COVID-19 standard MedDRA query (SMQ) narrow. All COVID-19 associated adverse events will be included in standard AE tables.

Treatment-emergent adverse events (TEAEs) are defined as adverse events occurring on or after the study treatment start date. A summary table providing an overview of COVID-19 associated TEAEs will be generated to include the number and percentages of subjects as well as the number of events in each of the following categories:

- Any TEAE through day 90
- Any TEAE through end of study
- TEAEs related to study treatment
- TEAE leading to infusion interruptions
- TEAE leading to permanent discontinuation of study treatment
- TEAE leading to study withdrawal
- Serious TEAEs
- Fatal TEAEs
- Fatal TEAEs related to study treatment

A listing showing all COVID-19 associated adverse events will be provided.

COVID-19 vaccine data collection

Sites will be prompted to inquire if subject has received a COVID-19 vaccination prior to or during study participation and to record each dose of the vaccine on the concomitant medications form along with the exact date of administration and manufacturer of the vaccine. Standardized Drug Grouping (SDG) from WHO Drug Dictionary will be utilized to identify COVID-19 vaccines. Any vaccination related adverse events experienced by study participants after informed consent will be recorded on the AE/SAE eCRF page.

The data are planned to be summarized as described below:

- Summary table by SoC and PT of all AEs occurring within 7 days after COVID-19 vaccine administration
- Listing of all AEs occurring within 7 days after COVID-19 vaccine administration
- Listing of all subjects receiving COVID-19 vaccine

Visit Modality, Missed Visits and Missing Assessments

The eCRF “Visit” page allows different options for visit modality (direct and indirect contact), as well as whether a visit is missed. The protocol requires in-person contact at all visits except at visits 7 and 10 when phone contact with subject is permissible. When a visit modality that deviates from the protocol is reported by investigator, an edit check is triggered in RAVE requesting the site to provide an explanation for the deviation. Site response to the query will be searched for character strings related to COVID-19 and if so identified, will be retained as alternate visit modality due to COVID-19 and merged with eCRF data by subject ID and visit. Since assessments (eg, vital signs, laboratory data) to be collected at each visit are known, the data missing due to COVID-19 can be determined using the approach described above.

Assessments that were missed or required alternate visit modality (eg, telephone with subject or indirect contact with family member or care taker) due to COVID-19 will be summarized. In addition, number of subjects with missed visits or alternate visit modality, by visit, will be summarized. A listing of visit modality by subject and visit will be provided.

Primary Efficacy Endpoint

A supplemental analysis of the primary endpoint will be undertaken to assess the impact of COVID-19 on the primary objective utilizing the estimand [[ICH E9 \(R1\)](#)] defined below. For subjects with a missed dose or treatment discontinuation due to COVID-19 impact, censoring will be applied 7 days after last infusion received on schedule. Subjects receiving no infusions due to COVID-19 impact will be censored at the time of randomization. In the context of this estimand, COVID-19 impact can be either COVID-19 infection or logistical constraints due to COVID-19. Analysis will use the same proportional hazards regression model as for the primary analysis.

Estimand

COVID-19 Estimand is defined as the hazard ratio for CSL112 vs. placebo, allowing for non-initiation, missed dose or discontinuation of treatment due to non-COVID reasons, in addition to standard of care as taken, for time to first occurrence of CV death, MI or stroke through 90 days in subjects with ACS presenting with STEMI or NSTEMI and MVD, while patients have not died due to non-CV causes.

Overview of COVID-19 Impact

Number and percentages of subjects experiencing at least one of the following outcomes due to COVID-19 will be summarized in an overview table:

- Subjects with Any COVID-19 Impact
- Missing one or more assessments
- Missing Visit
- Alternate Visit Modality
- Study Treatment Discontinuation
- Study Discontinuation
- Any TEAEs
- Any Serious TEAEs
- Fatal TEAEs
- Receipt of COVID vaccine

7.2 Multicenter Studies

Treatment assignment is planned to be stratified by region including North America, Latin America, Western Europe, Central and Eastern Europe, and Asia Pacific. Sites will be grouped according to region. A summary table of recruitment by region, country, and site will be produced. Statistical analysis of efficacy endpoints will be adjusted for region.

Summary tables, figures, and listings will not be reported by investigator site nor will investigator site be a factor in any statistical models.

